### 3. STUDY DESIGN

#### 3.1. GENERAL DESCRIPTION

A Phase II, randomized, 3-arm, placebo-controlled, partially blinded clinical trial that was conducted in 990 healthy HIV-uninfected, QFT-GIT negative, previously BCG vaccinated adolescents. Participants were recruited from high schools or directly from the community.

Participants were enrolled in two sequential cohorts:

- Safety and Immunogenicity Cohort:
  - o First 90 participants (30 from each arm).
  - o More intensive collection of safety data.
  - o Selected immunogenicity assays (including whole blood intracellular cytokine staining [ICS]).
  - o Data reviewed by the data monitoring committee (DMC), principal investigator and local medical monitor.
- Correlates Cohort:
  - o Remaining 900 participants.

All 990 participants in the study were evaluated for:

- Safety outcomes.
- Biomarker outcomes.
- Prevention of *Mtb* infection.

Within each cohort, participants were randomized in a 1:1:1 ratio to one of the following treatment groups:

- H4:IC31:
  - o 15 mcg H4/500 nmol IC31.
  - o Two doses (administered on Day 0 and Day 56).
  - o Intramuscular injection.
- Placebo:
  - o Saline volume equivalent to the H4:IC31 injection.
  - o Two doses (administered on Day 0 and Day 56).
  - o Intramuscular injection.

---

Document: Aeras\_C-040-404\_SAP\_V2\_0

Author: [name]

Version Number:

2.0

Version Date:

29SEP2017

Template No: CS\_TP\_BS016 – Revision 3

Reference: CS\_WI\_BS005

Effective Date: 01May2012

Copyright © 2012 Quintiles Transnational Corp. All rights reserved.

The contents of this document are confidential and proprietary to Quintiles Transnational Corp. Unauthorized use, disclosure or reproduction is strictly prohibited.

- BCG:
  - o 2-8 x 10^5 CFU.
  - o One dose (administered on Day 0).
  - o Intradermal injection.

Randomization to the H4:IC31 and Placebo treatment groups was double-blinded. Since BCG causes a recognizable local injection site reaction, the BCG revaccination treatment group was not blind. Laboratory staff performing QFT-GIT, immunogenicity and correlates assays were blinded to all three treatment groups. Planned randomization of participants is specified in Table 1: Planned Enrollment by Treatment Group and Cohort, below:

**Table 1: Planned Enrollment by Treatment Group and Cohort**

Cohort	Planned Number of Participants			
	Treatment Group			Total
	Placebo	BCG	H4:IC31	
Safety and Immunogenicity	30	30	30	90
Correlates	300	300	300	900
Total	330	330	330	990

BCG: Bacillus Calmette-Guerin.

Safety outcomes included solicited and unsolicited adverse events (AEs), injection site assessment, adverse events of special interest (AESIs) and serious adverse events (SAEs).

Each participant was followed for safety for a minimum of 6 months after the last vaccination.

The primary endpoint is:

- QFT-GIT conversion from negative to positive at any time point after Day 84 through end of follow-up in participants who were QFT-GIT negative at Study Day 84.

The secondary endpoint is:

- The primary endpoint occurrence (see aforementioned), persisting without QFT-GIT reversion from positive to negative through 6 months after QFT-GIT conversion.

The duration of the trial to primary analysis was endpoint-driven. The primary analysis was triggered when all of the following conditions were met:

- At least 64 primary endpoints were accrued in the study (regardless from which cohort).
- The median follow-up time was at least 15 months:
  - o Maximum individual follow-up time to detect QFT-GIT conversion of 24 months.

The protocol stated that if an initial reduction in infection rate in the BCG or H4:IC31 treatment group was seen in the primary analysis, follow-up for the entire study may be extended to examine the duration of prevention of *Mtb* infection. Following the primary analysis, there were no safety concerns of note. The DMC recommended that follow-up be continued as per protocol with a further DMC review close to the end of follow-up. Aeras confirmed that this second review by the DMC will only be completed following database (DB) lock. They also recommended that all participants have a QuantiFERON test performed at 24 months, including

Document: Aeras\_C-040-404\_SAP\_V2\_0

Author: [name]

Version Number:

2.0

Version Date:

29SEP2017

Template No: CS\_TP\_BS016 – Revision 3

Reference: CS\_WI\_BS005

Effective Date: 01May2012

Copyright © 2012 Quintiles Transnational Corp. All rights reserved.

The contents of this document are confidential and proprietary to Quintiles Transnational Corp. Unauthorized use, disclosure or reproduction is strictly prohibited.

all converters. The Sanofi Pasteur-Aeras Joint Steering Committee convened on June 14, 2016 and agreed to follow the DMC recommendations and to maintain study blind until study completion.

All participants with a primary endpoint (QFT-GIT conversion) were followed for an additional 6 months post-conversion to confirm whether they met the secondary or exploratory endpoints of sustained conversion or QFT reversion.

Participants who converted to a positive QFT-GIT at Month 6 or Month 12 were approached for a final QFT-GIT test and assessment for TB signs and symptoms at least 24 months after their initial vaccination.

The schedule for follow-up for individual participants was contingent on results of the QFT-GIT tests conducted at Month 3 (Day 84) and Months 6, 12, 18 and 24 study visits. A schematic of follow-up and QFT-GIT testing is presented in Figure 1: Schematic of Follow-up and QFT-GIT Testing, below.

[figure not shown]

Figure 1: Schematic of Follow-up and QFT-GIT Testing

\*Participants who converted at Month 6 or Month 12 were asked to return for a repeated QFT-GIT test done at least 24 months after their initial vaccination.

### 3.2. SCHEDULE OF EVENTS

The schedules of events for the BCG participants as well as the H4:IC31/Placebo participants are presented in Table 2: Schedule of Participant Evaluations (Participants Receiving BCG, N = 330) and Table 3: Schedule of Participant Evaluations (Participants Receiving H4:IC31 [N=330] or Placebo [N=330]), below.

Document: Aeras\_C-040-404\_SAP\_V2\_0  
 Author: [name]

Version Number: 2.0  
 Version Date: 29SEP2017

Template No: CS\_TP\_BS016 – Revision 3  
 Effective Date: 01May2012

Reference: CS\_WI\_BS005

**Table 2: Schedule of Participant Evaluations (Participants Receiving BCG, N = 330)**

Study Visit Day (D) or Month (M) →	Screen	0	D7	D28	D70	D84 c	M6 (D168) d,e M12 (D336) M18 (D504) M24 (D672)
Eligibility criteria verification	X	X					
Medical history	X						
Physical examination	X						
Urine βHCG (all females)	X	X					
QuantIFERON®-TB Gold in-tube (mL)	3					3	3
HIV-1 (mL) with HIV counselling	3						
Urinalysis	X		X b				
Serum chemistry (mL) f	5		5 b				
CBC, differential, platelets (mL)	5		5 b				
Vital signs	X	X					
Interval history		X	X	X	X	X	X
Focused physical examination a		X	X	X	X	X	X
Distribute/review diary cards		X b	X b				
Solicited adverse events (incl. con. meds.)		X	X				
Unsolicited adverse events (incl. con. meds.)		X	X	X			
SAEs, AESIs, and SUSARs (incl. con. meds.)		X	X	X	X	X	X
Solicited and unsolicited injection site reaction adverse events (incl. con. meds.)		X	X	X	X	X	
Site of injection examination		X	X	X	X	X	
TB symptom screen	X			X	X	X	X
BCG administration		X					
Whole blood assay (mL)		6 b			6 b		
Absolute blood count (mL)		0. 5	0. 5				0.5
RNA (mL)		2. 5	2. 5				2.5
PBMC for ICS (mL)		8 b			8 b		
Serum for multiplex ELISA (mL)		3 b	3 b				
PBMC, plasma, and serum for correlates of risk/protection (mL)		1 6			16		40 i
Whole blood for evaluation of novel IGRA (mL) 	7	7				7	7
PBMC for evaluation of NTM exposure (mL)		1 0					
Per visit phlebotomy volume (mL) h	23	5 3	16	0	32.5	10	53 (M6,M12)/ 13 (M18,M24)
Cumulative phlebotomy volume (mL) h	23	7 6	92	92	124.5	134.5	266.5

- If indicated by interval history
- Subjects in the Safety & Immunogenicity Cohort only
- Subjects who convert from QFT-GIT(-) to (+) at Day 84 will have a final visit at 168 days ±14 days after vaccination for assessment of SAEs, AESIs, SUSARs, and TB symptom screen
- Month 6, 12, 18, and 24 study visits will be completed by subjects who did not convert from QFT-GIT (-) to (+) at the previous visit; the Month 24 visit will be the final visit for subjects who remain QFT-GIT(-) throughout the study.
- Subjects who convert from QFT-GIT (-) to (+) at Month 6-24 visits will have two additional visits with repeat QFT-GIT testing, assessment of SAEs, AESIs, SUSARs, and TB symptom screen 84 days ±14 days and 168 days ±14 days after conversion. Up to 10 mL of blood will be collected at each of those visits, including blood for absolute blood count and RNA. Subjects who initially convert to QFT-GIT(+) at Month 6 or 12 will be asked to have a final QFT-GIT test, blood collection for absolute blood count and RNA, and TB symptom screen done at least 24 months after their initial vaccination.
- May not be collected at all time points shown.
- Serum chemistry includes AST, ALT, alkaline phosphatase, total bilirubin, creatinine, and BUN.
- Blood volumes are approximate.
- Study Months 6 and 12 only.

**Table 3: Schedule of Participant Evaluations (Participants Receiving H4:IC31 [N=330] or Placebo [N=330])**

Study Visit Day (D) or Month (M) →	Screen	0	D3	D7	D28	D56	D63	D70	D84 c	M6 (D168) d,e M12 (D336) M18 (D504) M24 (D672)
Eligibility criteria verification	X	X				X				
Medical history	X									
Physical examination	X									
Urine βHCG (all females)	X	X				X				
QuantIFERON®-TB Gold in-tube (mL)	3								3	3
HIV-1 (mL) with HIV counselling	3									
Urinalysis	X			X b			X b			
Serum chemistry (mL) f	5			5 b			5 b			
CBC, differential, platelets (mL)	5			5 b			5 b			
Vital signs	X	X				X				

Document: Aeras\_C-040-404\_SAP\_V2\_0

Author: [name]

Version Number:

2.0

Version Date:

29SEP2017

Template No: CS\_TP\_BS016 – Revision 3

Reference: CS\_WI\_BS005

Effective Date: 01May2012

Copyright © 2012 Quintiles Transnational Corp. All rights reserved.

The contents of this document are confidential and proprietary to Quintiles Transnational Corp. Unauthorized use, disclosure or reproduction is strictly prohibited.

Study Visit Day (D) or Month (M) →	Screen	0	D3	D7	D28	D56	D63	D70	D84 c	M6 (D168) d,e M12 (D336) M18 (D504) M24 (D672)
Interval history		X	X	X	X	X	X	X	X	X
Focused physical examination a		X	X	X	X	X	X	X	X	X
Distribute/review diary cards		X b		X b		X b	X c			
Solicited adverse events (incl. con. meds.)		X	X	X		X	X			
Unsolicited adverse events (incl. con. meds.)		X	X	X	X	X	X	X	X	
SAEs, AESIs, and SUSARs (incl. con. meds.)		X	X	X	X	X	X	X	X	X
Solicited injection site reaction adverse events (incl. con. meds.)		X	X	X	X	X	X	X	X	
Site of injection examination		X	X	X	X	X	X	X	X	
TB symptom screen	X				X	X			X	X
Study vaccine administration		X				X				
Whole blood assay (mL)		6 b						6 b		
Absolute blood count (mL)		0.5	0.5							0.5
RNA (mL)		2.5	2.5							2.5
PBMC for ICS (mL)		8 b						8 b		
Serum for multiplex ELISA (mL)		3 b	3 b							
PBMC, plasma, and serum for correlates of risk/protection (mL)		16						16		40 f
Whole blood for evaluation of novel IGRA (mL) g	7	7							7	7
PBMC for evaluation of NTM exposure (mL)		10								
Per visit phlebotomy volume (mL) h	23	53	6	10	0	0	10	32.5	10	53 (M6,M12)/ 13 (M18,M24)
Cumulative phlebotomy volume (mL) h	23	76	82	92	92	92	102	134.5	144.5	276.5

- If indicated by interval history
- Subjects in the Safety & Immunogenicity Cohort only
- Subjects who convert from QFT-GIT(-) to (+) at Day 84 will have a final visit at 168 days ±14 days after second vaccination (Month 8, Study Day 224) for evaluation of SAEs, AESIs, SUSARs, and TB symptom screen
- The Month 6, 12, 18, and 24 study visits will be completed by subjects who did not convert from QFT-GIT (-) to (+) at the previous visit; the Month 24 visit will be the final visit for subjects who remain QFT-GIT(-) throughout the study
- Subjects who convert from QFT-GIT (-) to (+) at Month 6-24 visits will have two additional visits with repeat QFT-GIT testing, assessment of SAEs, AESIs, SUSARs, and TB symptom screen 84 days ±14 days and 168 days ±14 days after conversion. Up to 10 mL of blood will be collected at each of those visits, including blood for absolute blood count and RNA. Subjects who initially convert to QFT-GIT(+) at Month 6 or 12 will be asked to have a final QFT-GIT test, blood collection for absolute blood count and RNA, and TB symptom screen done at least 24 months after initial vaccination.
- May not be collected at all time points shown.
- Serum chemistry includes AST, ALT, alkaline phosphatase, total bilirubin, creatinine, and BUN.
- Blood volumes are approximate.
- Study Months 6 and 12 only.

### 3.3. CHANGES TO ANALYSIS FROM PROTOCOL

- On page 23 of the protocol, the following is stated: “The secondary analysis will be triggered after 6 months of additional post-conversion follow-up for individuals who convert, regardless of the rate of QFT-GIT reversion.”

Following discussions with Aeras, it was clarified that there will not be any formal secondary analysis. Following the primary analysis there will only be one additional analysis, the final analysis. The final analysis will occur once all planned follow-up visits have been completed, or following the termination of the trial (if terminated before the required follow-up visits occurred).

- On page 52 of the protocol the Intent-to-treat analysis set is defined as: “The intent-to-treat population for efficacy and immunogenicity analyses will consist of all randomized subjects.”

Following discussions with Aeras, it was decided that since the Intent-to-treat analysis set is the same as the Randomized analysis set, a Modified Intent-to-treat analysis set will be defined and used for analysis purposes.

The Modified Intent-to-treat analysis set is defined as described in Section 5.3: Modified Intent-to-treat Analysis Set.

Document: Aeras\_C-040-404\_SAP\_V2\_0

Author: [name]

Version Number:

2.0

Version Date:

29SEP2017

Template No: CS\_TP\_BS016 – Revision 3

Reference: CS\_WI\_BS005

Effective Date: 01May2012

Copyright © 2012 Quintiles Transnational Corp. All rights reserved.

The contents of this document are confidential and proprietary to Quintiles Transnational Corp. Unauthorized use, disclosure or reproduction is strictly prohibited.

- The following exploratory analyses will not be performed as part of this SAP, as agreed by Aeras:
  - o Identifying immune correlates of risk for *Mtb* infection.
  - o Evaluating alternative IGRAs or immune markers for diagnosis of *Mtb* infection or as markers of exposure to nontuberculous mycobacteria (NTM).
  - o Identifying immune correlates of vaccine-induced protection against *Mtb* infection induced by H4:IC31 or BCG revaccination.
  - o Exploring trends in TB disease incidence after vaccination.

Aeras and some of its external partners will prepare a separate correlates SAP once the trial's efficacy results become available.

- On 5 April 2016, Aeras Biostatistics and Data Management were notified of a manufacturer's recall of a portion of the QuantiFERON (QFT) tubes that were used in determination of endpoints. The recall primarily stemmed from changes in Qiagen's quality control (QC) process, which resulted in their recalling all unexpired partial lots that had been previously circulated for use. Although Qiagen's ongoing QC processes did not detect a spike in false positive results within this partial lot, they were unable to rule out the possibility of false positive results coming from the tubes in question, thereby resulting in the recall.
  - o Sixteen (16) positive QFT results came from these recalled tubes, affecting 14 unique participants. Nine (9) of the tubes contributed toward the trial's primary efficacy endpoint. Even though the information provided by Qiagen does not suggest that these results are false positives, the tubes were recalled nonetheless. Therefore, in an abundance of caution, Aeras considered an additional analysis set that would remove these results from the primary endpoint and final endpoint analysis.

Aeras requested the following approach to handle this:

- o Create an additional analysis set (refer to Section 5.4: Adjusted Modified Intent-to-treat (first recall positive omit Analysis Set)).
- o Perform the following additional analysis:
  - Modified Intent-to-treat (mITT) with adjudication: This analysis will retain QFT data from all visits for participants who received positive QFT results from recalled tubes provided they also received positive results from non-recalled tubes. In other words, if a participant has positive QFT results from both non-recalled and recalled tubes, then all of these results will be treated as true positives.
- Whilst setting up the programming for the medical review listings, Data Management (DM) was requested to use the following toxicity criteria for Urine Erythrocytes since this is recorded as a qualitative value and the protocol provides the toxicity criteria for quantitative values. These criteria will be used to determine the toxicity grading. ++/+++ values will therefore be regarded as 'Grade 2/3/4'.

Laboratory Test	Grade 1	Grade 2	Grade 3	Grade 4
Urine Erythrocytes	+	++/+++	++/+++	++/+++

Document: Aeras\_C-040-404\_SAP\_V2\_0

Author: [name]

Version Number:

2.0

Version Date:

29SEP2017

Template No: CS\_TP\_BS016 – Revision 3

Reference: CS\_WI\_BS005

Effective Date: 01May2012

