The duration of the trial will be endpoint-driven, using a design targeting accrual of 64 primary endpoints. The primary analysis will be triggered when at least 64 endpoints are accrued in the study (both cohorts) AND the median follow up time is at least 15 months, with a maximum individual follow-up time to detect initial QFT-GIT conversion of 24 months. Enrollment is expected to take approximately 12 months and the primary analysis is expected to occur approximately 21 months from the first subject enrolled. Therefore, duration of individual subject follow-up for the primary analysis is expected to range from 9 – 21 months (maximum 24 months), with 6 months of additional follow up for those who convert to QFT-GIT positive after Day 84 as shown in Figure 2-1. If an initial reduction in infection rate in the BCG or AERAS-404 groups is seen in the primary analysis of QFT-GIT conversion, follow up for the entire study may be extended to examine the duration of prevention of *Mtb* infection.

The trial sample size of 990 subjects is determined by the primary prevention of *Mtb* infection objective (measured by prevention of conversion to a positive QFT-GIT test). A potential mechanism of action of vaccination might be to allow initial *Mtb* infection (and QFT-GIT conversion), but to prevent establishment of sustained latent *Mtb* infection (and thus persistent

QFT-GIT conversion), resulting in QFT-GIT reversion to negative. Thus the study will also examine the persistence of QFT-GIT conversion.

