### 5.1.4 Data Monitoring Committee

The DMC will operate according to its charter. If study vaccine administration is paused by the local medical monitor or the principal investigator, the DMC will be convened. Based on its review and the protocol stopping rules (Section 6.2) the DMC will make recommendations in the DMC minutes to Aeras regarding further conduct of the study and further administration of study vaccine. The DMC may review an individual SAE or it may choose to review adverse events, serious adverse events, solicited adverse events, and laboratory and vital signs data. The DMC may unblind any amount of safety information needed to conduct their assessment. All procedures associated with this review, including objectives, data handling, and elements to be included for review will be documented in DMC minutes. The DMC may recommend suspension or resumption of enrollment and study vaccine administration after review of safety data. However, the sponsor will make the final decision to suspend or resume study activities. The recommendations of the DMC, along with the sponsor's decision, will be communicated to the investigators and the IRB/Ethical Committees and the national regulatory authorities. The sponsor or its designee agrees to abide by any directives issued by the national regulatory authority or the Institutional Review Board.

The DMC will review safety data for the Safety & Immunogenicity cohort as described in Section 2.2. The DMC will also review unblinded data after sufficient QFT-GIT conversion endpoints have accumulated for the primary analysis of prevention of infection with *Mtb*, and if an impact on infection (positive or negative) is seen will advise the Sponsor accordingly. The Sponsor may then elect to extend follow up of all subjects to explore the duration of prevention of infection after vaccination, or to terminate the study.

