### 7.3 Prevention of Infection (QFT-GIT Conversion) Analyses

The primary *Mtb* infection endpoint will be QFT-GIT conversion from a negative to positive test, using the manufacturer's recommended threshold of 0.35 IU/mL, at any time-point after Day 84 and through end of follow-up for the primary endpoint (see below). The frequency of QFT-GIT negativity/positivity will be summarized for each treatment group at screening, on Day 84, on Month 6, and for all subsequent assessments. The log-rank statistic will be used to test the null hypothesis of no difference in the rates of *Mtb* infection over the follow-up period between each of the AERAS-404 and BCG groups compared to the placebo group. The log-rank test statistic compares estimates of the hazard functions of the vaccine groups at each observed event time. It is constructed by computing the observed and expected number of events in the groups at each observed event time and then summing these to obtain an overall summary across all time points where there is an event. As subjects convert their QFT-GIT tests over time (experience a primary endpoint) or are lost to follow up the number of subjects at risk over time will change. As this is a proof of concept study, these two log-rank tests (AERAS-404 compared to placebo and BCG revaccination compared to placebo) will be performed with a 1-sided Type 1 error of 0.1. There will be no adjustment for multiplicity to control the Type 1 error rate over the two tests. The rationale for not performing this adjustment is related to the fact that the tests pertain to efficacy assessments of two unrelated vaccines. If these two evaluations were performed in two separate trials then no adjustment for multiplicity would be made. Thus, one should not be compelled to adjust for this multiplicity simply because the two evaluations are performed administratively in a single trial.

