## 7.6 Sample Size Considerations

Sample size for the trial is based on the power to detect a reduction in the rate of infection with *Mtb*, as determined by QFT-GIT conversion. As a proof of concept study looking for evidence of biologic impact, the trial is designed to distinguish a QFT-GIT conversion rate reduction of 50% compared to placebo for each vaccine (AERAS-404 and BCG) with power of 80% and a type 1 error rate of 10% (1-sided).

Trial design calculations are performed by computer simulation. The simulations estimate the statistical operating characteristic of a conditional binomial test which, due to relative rarity of the endpoint, provides an excellent approximation to the operating characteristic of the log-rank tests which will be used in the analyses of trial data. The following assumptions, based on preliminary data from SATVI (Mahomed et al, 2011b) were used in these simulations:

- Primary *Mtb* infection endpoint rate = 10% per year
- Rate of loss to follow up = 7% per year
- Average rate of enrollment = 20 subjects per week
- Maximum duration of follow up to primary conversion = 24 months with 6-monthly study visits

Under these assumptions, a total sample size of 990 is expected to provide 64 primary QFT-GIT conversion endpoints approximately 21 months after the first subject is enrolled. Follow up will continue until 64 endpoints are accrued and a median follow up duration of 15 months for individual subjects have both occurred. A 10% rate of QFT-GIT conversions per year is conservative (SATVI data have shown an average 17% conversion rate in adolescents); however, continuing to follow subjects until the required number of endpoints is accrued ensures adequate power for the primary endpoint.

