## 7.7 Plan for Statistical Summaries and Analyses

### 7.7.1 Primary Data Review

After 64 primary QFT-GIT conversion endpoints and a median of 15 months follow up have both occurred a primary unblinded analysis of QFT-GIT conversion data will be conducted by an independent statistical group and results will be reviewed by the DMC. If an effect on QFT-GIT conversion is seen, follow up for the entire study cohort may be extended. Study investigators will remain blinded to treatment assignments for the duration of study follow up.

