## 4. PLANNED ANALYSES

The following formal analyses will be performed for this study:

- Day 7 DMC.
- Day 84 DMC.
- Primary analysis.
- Final analysis.

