### 4.2. PRIMARY ANALYSIS

The primary analysis, based on a separate SAP and set of TLF shells was completed once the following two conditions were met:

- At least 64 primary endpoints had accrued (refer to Section 14.1.1: Primary Efficacy Endpoint for a description of the primary endpoints).
- The median follow-up time (for all participants in the Modified Intent-to-treat [mITT] analysis set) from Day 0 was at least 15 months.

The DMC received the primary analysis report and provided a recommendation to the study sponsor regarding whether to continue, stop or modify the trial as currently planned.

---

Document: Aeras\_C-040-404\_SAP\_V2\_0  
Author: [name]

Version Number: 2.0  
Version Date: 29SEP2017

Template No: CS\_TP\_BS016 – Revision 3  
Effective Date: 01May2012

Reference: CS\_WI\_BS005

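### Does re-testing the primary endpoint at the final analysis break the one-sided 10% error set for the 64-endpoint primary analysis?

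*SAP*

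**What the plan says.** Protocol 2.2 ties the primary analysis to two conditions: 64 endpoints and a median follow-up of 15 months. Protocol 7.3 states that the two log-rank tests "will be performed with a 1-sided Type 1 error of 0.1". Protocol 7.6 sizes the trial for a 50% reduction per vaccine, with 80% power at that error rate. Under Protocol 7.7.1, once both conditions are met, "a primary unblinded analysis of QFT-GIT conversion data will be conducted by an independent statistical group" and the DMC reviews the result. Protocol 5.1.4 adds that the DMC "if an impact on infection (positive or negative) is seen will advise the Sponsor accordingly", after which the sponsor may extend follow-up or stop.

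SAP 4 begins its list with "The following formal analyses will be performed for this study" and names the primary and final analyses separately. SAP 4.2 puts the first in the past: "The primary analysis, based on a separate SAP and set of TLF shells was completed once the following two conditions were met". SAP 3.3 then says "Following the primary analysis there will only be one additional analysis, the final analysis". That sentence replaces the protocol's separate secondary analysis. SAP 14.1.2, under the primary endpoint, lists hazard ratios, one-sided log-rank p-values and 80% two-sided intervals. SAP 7.4 explains why there is no adjustment across the two vaccines and adds that the study seeks no definitive claims. It does not mention the two analysis times.

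**The concern.** The same hypothesis is tested twice on accumulating data. The first test was unblinded to the DMC, the second uses the same statistic, and no error is spent between them. The visible SAP never calls the second test supportive, and both analyses are described as formal. If they disagreed, a reader of this SAP alone would find no sentence saying which one stands.

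The verdict on each vaccine has consequences. Correlates assays follow if an effect on infection is seen (Protocol 7.4.2.3), larger studies would be justified (Protocol 1.7), and placebo recipients may be offered an effective vaccine (Protocol 9.1). A choice between two p-values made after both were known would lose the stated 10% error.

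**Working it through.** **1. Reproduce the plan's own figure.** Inputs from Protocol 7.6: hazard ratio 0.5, one-sided 0.10 (z = 1.2816), power 80% (z = 0.8416), 64 endpoints over three equal arms.

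- Events needed per vaccine–placebo pair: 4 × (1.2816 + 0.8416)² / (ln 0.5)² = 37.5, so 38.
- If one vaccine works, endpoints split 1 : 0.5 : 1 and the pair has 64 × 1.5/2.5 = 38.4.
- Power = Φ(0.6931 × √(38.4/4) − 1.2816) = Φ(2.148 − 1.282) = 0.807.
- If both work, the pair has 64 × 1.5/2 = 48 and power is 0.869.

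Simulation with the protocol's inputs (10% conversion per year, 7% loss per year, 20 enrolled per week, one effective vaccine) puts the 64th endpoint at a median of 21.8 months, with 80.8% power. The protocol's 80% and roughly 21 months both hold.

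**2. Error if success at either analysis counted.** Either-analysis error = 1 − P(Z₁ < 1.2816, Z₂ < 1.2816). Z₁ and Z₂ are standard normal with correlation √t, where t is first-analysis events divided by final events. The documents give no event counts, so t is an assumption.

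| t | 0.40 | 0.50 | 0.52 | 0.57 | 0.66 | 0.80 | 0.90 |
|---|---|---|---|---|---|---|---|
| error | 0.159 | 0.153 | 0.151 | 0.148 | 0.142 | 0.132 | 0.122 |

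Simulations at the design rates with no vaccine effect give about 69 to 79 endpoints at the first analysis and 132 to 138 at the end. There t is 0.52 to 0.57, and the simulated either-analysis error is 0.15 to 0.16.

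**3. Error if one analysis decides.** It is 0.10 per vaccine, whichever analysis is chosen, provided the choice does not depend on the results.

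**4. What disagreement consists of.** Take the log-rank mean as −ln(HR) × √(d/4). First-analysis pair counts are set at exactly 64 endpoints; final pair counts come from simulation at the design rate.

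| Case (one effective vaccine) | d, first / final | Power, first | Power, final | Either | First only | Final only | Disagree |
|---|---|---|---|---|---|---|---|
| Efficacy 50% | 38.4 / 70.2 | 0.807 | 0.948 | 0.957 | 0.010 | 0.151 | 0.160 |
| Efficacy 30% | 40.3 / 79.5 | 0.441 | 0.621 | 0.674 | 0.053 | 0.233 | 0.286 |

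First only is either minus final power; final only is either minus first power. Simulation gives somewhat less disagreement at 30% efficacy (24% to 27%) and about the same at 50% (15% to 16%). With no effect, disagreement at t = 0.52 is 2 × (0.151 − 0.100) = 0.10. When a vaccine works, most of the disagreement is the larger data set detecting an effect the smaller one missed.

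**5. Which analysis decides, from the texts.**

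- Protocol 2.2 and 7.7.1 name the 64-endpoint analysis primary, and 7.6 attaches the error and power to it.
- The available text of SAP 3.3, the section for departures from the protocol, declares no change to that.
- SAP 14.1.2 asks for p-values and intervals but sets no significance level or success rule. The 0.10 is inferred from the 80% interval and the protocol.
- SAP 3.1 records that, after the first analysis, the DMC advised continuing as per protocol and the joint steering committee agreed to keep the blind to study completion. Nothing visible shows the first result being used to claim success.

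**The case for a change.** The strongest case for a change runs as follows. This SAP governs the final study report, so it should say which p-value carries the inference. It also points both ways. The protocol makes the 64-endpoint test primary, yet SAP 3.3, written after that test was run, speaks of a later correlates SAP once efficacy results are available, which suggests the final analysis supplies them. Lock and unblinding are still ahead in SAP 4.3, so one sentence would cost almost nothing. Seeking no definitive claims lowers the stakes but gives neither test a role.

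It stands that no visible sentence labels the final result, and that SAP 7.4 is silent on the two times. The rest does not amount to a defect. A label calling the first test decisive would restate Protocol 7.6 and 7.7.1. It may already sit in the separate primary-analysis SAP (SAP 4.2) or the Primary Analysis Note to File (SAP 18), neither of which is among these documents.

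Making the final result merely supportive is also open to argument. The endpoint runs to the end of follow-up, and the final analysis has about 94% to 95% power at 50% efficacy, against about 80% at the first with one effective vaccine. Reasonable statisticians would differ on which should lead.

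**Conclusion.** No change follows. The gap is a missing label that analysts can fill from the protocol: the 64-endpoint analysis is primary, and the final analysis reports the same endpoint on complete follow-up. No sample size, power or stated error rate is wrong.

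The inflation to about 15% per vaccine at the design rates (12% to 16% for t from 0.9 to 0.4) needs a rule that success at either analysis counts, and no passage states one. The disagreement figures apply a 0.10 cut-off that the SAP does not set for the final analysis. The stakes are further limited because this is a proof-of-concept trial.

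This conclusion rests on two assumptions. The first is that the documents not available here do not contradict the protocol. The second is that the report keeps the protocol's designation: treating the final test as decisive instead would be a change from Protocol 7.6 and 7.7.1, to be declared as such.
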